4.2. Study Design

This is a prospective, open label trial evaluating home telemonitoring for patients with COPD and a history of increased exacerbation risk. The purpose of this study is to determine whether automated home monitoring of medication compliance and biometric parameters (FEV1, FVC, PIFR, IC, pulse oximetry, and symptoms) is acceptable to patients, can improve adherence, and may improve clinical outcomes and reduce exacerbations and avoidable 30-day readmissions. Slow spirometry will be performed Sundays, Mondays, Wednesdays, Fridays and Saturdays. Forced spirometry will be performed Tuesdays and Thursdays.

5. Study Endpoints

5.1. The specific Primary Endpoints of this study are:

- Adherence to measurement collection
- Quality of Life scores

5.2. The specific Secondary Endpoints of this study are:

- Variability in slow spirometry and correlation of change in slow spirometry values with COPD exacerbation
- Patient satisfaction with the monitoring system
- Thirty (30) day exacerbations
- Total number of clinical interventions by type (what the medical staff does in response to the telemonitoring)
- Ability for early identification of loss of DPI effectiveness
- Adherence to taking prescribed medications

6. Selection of Study Population

Eligible participants include those being managed for COPD by the UNC Hospitals Pulmonary Specialty Clinic in Chapel Hill, NC and who have been identified to be at a higher risk of exacerbation of their COPD. We plan to enroll twelve (12) patients for three (3) months of monitoring each. The study will be at a single center and anticipated to be completed within nine (9) months.

6.1. Inclusion Criteria:

- Male or Female patients
- 40 to 80 years of age
- English
- Spirometry confirmed COPD (post-BD FEV1/FVC<0.70) and post-BD FEV1% predicted <80% at screening visit. (Target 50% of recruitment with post-BD FEV1<50% predicted (severe obstruction). Spirometry must have been collected within 24 months prior to screening.
- Increased COPD exacerbation risk defined as either of the following in the prior 12 months:
 - One hospitalization for COPD exacerbation
 - Two outpatient COPD exacerbations requiring treatment with steroids and/or antibiotics
- Signed informed consent

6.2. Exclusion Criteria:

- Unable to perform spirometry on their own following training.

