The secondary endpoints will be reported as proportion with 95% confidence interval of participants with score of 4 or higher on individual survey domains of patient satisfaction summary score; Descriptive analysis of patient satisfaction summary scores will include mean (SD), median (IQR), range of scores.

For the COPD exacerbation analyses, the proportion of patients with COPD exacerbations and the rate of exacerbations occurring during follow-up will be reported along with 95% CI. A patient will be considered censored for exacerbations at the time of the last documented visit, the end of the study, or death (whichever occurs earlier), if they did not experience an exacerbation before.

Exploratory Endpoints Definitions

The study contains exploratory endpoints to examine individual components of the monitoring functions and their impact. These include:

- Rate of self-reported COPD exacerbations stratified by FEV1 and defined as the 30-day COPD exacerbation rate, defined as the mean number of self-reported COPD exacerbations

requiring treatment with antibiotics or steroids per 30 days of follow-up (averaged using 3 months of follow-up data), stratified by FEV1 (separately <50% predicted and >=50% predicted).

- Home spirometry measurement collection adherence defined as the percentage of participants achieving >50% completion of spirometry measurements over three months.
- Home pulse oximetry measurement collection adherence defined as the percentage of participants achieving >50% completion of pulse oximetry over three months.
- Home questionnaire collection adherence defined as the percentage of participants achieving >50% completion of home questionnaires over three months.
- Quality of home forced spirometry measures defined as the percentage of forced home spirometry measurements that meet ATS quality standards
- Change from baseline on COPD Assessment Test (CAT) Total Score defined as the CAT scores measured at baseline, week 4, week 8 and week 12 and the median (SD) change in CAT score from baseline will be calculated at each time point.
- Inspiratory Capacity variability defined as the coefficient of variation will be calculated by dividing standard deviation of Inspiratory Capacity values by the mean of the inspiratory capacity values. Inspiratory capacity measured via slow vital capacity maneuver will be performed at home five days per week during duration of study.

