- Inspiratory Capacity before, during and after COPD exacerbations defined as the overall median Inspiratory Capacity reported at three time intervals: the week before COPD exacerbation, the week of COPD exacerbation, and the week after COPD exacerbation.
- Number of clinical interventions defined as the total number of clinical interventions per participant over study duration. Clinical interventions will be categorized into one of three types (phone contact, clinic visit, referral to Emergency Department).
- Type of clinical interventions defined as the percentage of type of clinical intervention across all study participants. Clinical interventions will be categorized into one of three types (phone contact, clinic visit, referral to Emergency Department).
- Suboptimal peak inspiratory flow measurements defined as the percentage of peak inspiratory flow measurements <3.27 liter/sec obtained on forced spirometry maneuvers.
- Maintenance inhaler adherence defined as the adherence will be defined by average number of days per week (range 0-7) participant reports maintenance inhaler use.
- Change from baseline in maintenance inhaler adherence defined as the change from baseline to 3 months in maintenance inhaler adherence. Adherence will be defined by number of days per week (range 0-7) participant reports maintenance inhaler use.
- Change from baseline in rescue inhaler use defined as the change from baseline to 3 months in rescue inhaler use. Rescue inhaler use will be categorized at baseline and 3 month visit as not at all, once a week or less, 2-3 times per week, 1-2 times per day, 3 or more times per day.

Analysis of Exploratory Endpoints

The exploratory endpoints will be analyzed as described below. The hypothesis testing of these additional secondary efficacy endpoints is considered exploratory. All tests with p value < 0.05 will be interpreted nominally as statistically significant.

- For stratified COPD exacerbation analyses, the proportion of patients with COPD exacerbations and the rate of exacerbations occurring during follow-up will be reported along with 95% CI stratified by FEV1 severity (<50% predicted: >=50% predicted).
- Individual home assessment component adherence will be reported as proportions with 95% confidence intervals
- Quality of home forced spirometry measures will be reported as proportions with 95% confidence intervals

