- Descriptive analysis of change from baseline to weeks 4, 8 and 12 on CAT Total score including mean (SD), median (IQR), range
- Descriptive analysis of Inspiratory Capacity measurements, including mean (SD), median (IQR), range, coefficient of variation
- The overall median of Inspiratory Capacity in the week before, of, and after each exacerbation will be calculated and compared using Kruskall-Wallis testing.
- The total number and distribution of type of intervention (phone contact, clinic visit, referral to Emergency Department) will be summarized in tabular format
- The proportion of suboptimal peak inspiratory flow measurements (defined as <3.27L/sec) will be reported with 95% CI. Additional exploratory analyses include distribution of peak inspiratory flow measurements along with proportions of alternative thresholds.
- Descriptive analysis of overall maintenance inhaler adherence including mean (SD), median (IQR), range, proportion and 95% CI of participants with >50% adherence
- Descriptive analysis of change from baseline to week 12 on number of days per week of maintenance inhaler adherence including mean (SD), median (IQR), range
- Tabular summary of overall rescue inhaler use (categorized into not at all, once a week or less, 2-3 times per week, 1-2 times per day, 3 or more times per day)
- Comparative analysis (chi square) of distribution of categorical responses to rescue inhaler use comparing baseline to 12 week visit
- Tabular summary of number and type of SAE

14. Safety Monitoring

As this study is deemed low risk, using technology frequently prescribed for use by COPD patients at home, oversight for this feasibility study will be conducted by the PI ([name]). The PI will monitor data to ensure the safety of participants. Only treatment-related serious adverse events (SAEs) will be reported to the IRB using the Adverse Event Template Form, per institutional and national guidelines within one business day of notification of the event. Hospitalization for COPD exacerbation will be considered an SAE. SAEs will be tracked for 30 days following termination of the study.

15. Administrative Requirements

15.1. *Ethical Considerations*

The study will be conducted in accordance with the ethical principles founded in the Declaration of Helsinki, and according to local applicable laws and regulations. The institutional

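### Two exploratory percentages count repeated measurements from 12 patients, yet no interval method is named; a pooled binomial 95% CI would be too narrow if results cluster within patients

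*Combined protocol and SAP*

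**What the plan says.** Section 13 defines suboptimal peak inspiratory flow as the "percentage of peak inspiratory flow measurements <3.27 liter/sec obtained on forced spirometry maneuvers", and spirometry quality as the "percentage of forced home spirometry measurements that meet ATS quality standards". In both, the denominator is a count of measurements.

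The analysis part of the section gives one line for each: "The proportion of suboptimal peak inspiratory flow measurements (defined as <3.27L/sec) will be reported with 95% CI", and "Quality of home forced spirometry measures will be reported as proportions with 95% confidence intervals". For peak flow it adds: "Additional exploratory analyses include distribution of peak inspiratory flow measurements along with proportions of alternative thresholds".

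The neighbouring adherence endpoints use a different unit. Spirometry adherence, for example, is the "percentage of participants achieving >50% completion of spirometry measurements over three months", so each patient counts once.

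On size, Section 6 says: "We plan to enroll twelve (12) patients for three (3) months of monitoring each". Sections 7.4 and 9.2.3 give 12 weeks of active monitoring with forced spirometry on two days a week.

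The document names no method for these intervals and does not mention dependence between measurements from the same patient.

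**The concern.** A proportion of measurements reported with a 95% CI reads most naturally as a binomial interval on the pooled count. That interval treats every measurement as independent. Here a few hundred measurements would come from 12 patients, and results from one patient may resemble each other.

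The argument is stronger for peak flow. Each patient's values are compared with one fixed cut-off, so a patient whose usual flow lies well to one side of it will give nearly the same answer every time. The protocol itself treats lung function as patient-specific: the alerts in Section 8 use personalised z-scores. Section 4.1 reports small day-to-day variation in an earlier study on the same platform. That was a transplant population and peak inspiratory flow is not mentioned, so it is supportive only. For spirometry quality the correlation may be low.

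At stake is how well established the two rates appear. Section 13 intends the study's results, without singling out these two, to show up faults in the technology and to help size later studies. An interval that is too short would suggest more knowledge than 12 patients can supply.

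**Working it through.** **Inputs.** 12 patients (Section 6); 2 forced-spirometry days a week (Section 9.2.3 and footnote c of Section 17); 12 weeks (Section 7.4). Scheduled sessions per patient: 2 × 12 = 24. In total: 12 × 24 = 288. The plan gives no expected rate, precision or intraclass correlation (ICC) for these endpoints, so it has no figure of its own to reproduce. The rates and ICCs below are assumptions, shown over a range.

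**Step 1: design effect.** DE = 1 + (m − 1) × ICC with m = 24. The effective number of independent measurements is 288/DE, and a pooled interval must be widened by √DE. At a rate of 80% the pooled half-width is 1.96 × √(0.8 × 0.2/288) = 4.6 points, whatever the ICC. The last column replaces 1.96 with the t quantile on 11 df and multiplies by √DE.

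| ICC | DE | Effective n | √DE | Half-width at 80%, t(11) |
|---|---|---|---|---|
| 0.05 | 2.15 | 134 | 1.47 | 7.6 points |
| 0.1 | 3.3 | 87 | 1.82 | 9.4 points |
| 0.3 | 7.9 | 36 | 2.81 | 14.6 points |
| 0.5 | 12.5 | 23 | 3.54 | 18.3 points |

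**Step 2: coverage.** Beta-binomial simulation, 12 patients, 200,000 replicates per setting. The pooled Wilson interval is compared with the participant-based logit interval set out under the fix. Entries are percent coverage of a nominal 95% interval at ICC 0.05 / 0.1 / 0.3 / 0.5.

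| True rate; sessions per patient | Pooled Wilson | Participant-based |
|---|---|---|
| 80%; 24 | 81 / 71 / 50 / 40 | 95 / 95 / 95 / 94 |
| 80%; 12 | 89 / 83 / 66 / 55 | 96 / 96 / 95 / 95 |
| 80%; 6 to 24, unequal | 86 / 78 / 58 / 48 | 95 / 95 / 94 / 94 |
| 30%; 24 | 81 / 71 / 50 / 41 | 95 / 95 / 96 / 96 |
| 90%; 24 | 83 / 72 / 51 / 41 | 95 / 95 / 92 / 88 |
| 95%; 24 | 81 / 71 / 48 / 34 | 94 / 93 / 86 / 78 |

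Samples at exactly 0% or 100%, where the logit interval does not exist, count as misses for it. The unequal row assumes that how many sessions a patient completes is unrelated to that patient's rate.

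**Step 3: no correlation.** At ICC 0 (40,000 replicates per setting) Wilson covers 94.4 to 95.4% and the participant-based interval 95.2 to 97.3%. The latter is then 1.09 to 1.11 times as wide.

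**Step 4: does an exact interval help?** No. At a rate of 80% and 24 sessions, Clopper-Pearson covers 82.5 / 72.2 / 51.6 / 41.3% at the same four ICCs. The fault lies in the independence assumption, not in the binomial approximation.

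**Step 5: what counts as a measurement?** The plan does not say whether it is a session or a single manoeuvre. If three manoeuvres per session were counted (an assumption), m = 72 and √DE becomes 2.13 / 2.85 / 4.72 / 6.04. Counting the forced spirometry from the training call (Section 7.4) makes m = 25 and changes little: 1.48 / 1.84 / 2.86 / 3.61.

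**The case against.** The strongest reply is that no wrong analysis has been shown. The plan never says binomial, and it names no interval method for any endpoint, the primary proportions included. An analyst could use a clustered interval and still be following it. That stands: this is an omission, and the harm depends on how it is filled. But the silence matters more here than elsewhere. Where each patient counts once, any standard binomial interval is defensible; where each contributes up to 24 results, it is not. Nor does the rest of Section 13 suggest that dependence will be handled. It plans Kruskal-Wallis across the weeks around an exacerbation and a chi-square test of baseline against week 12, both on results from the same patients.

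The second reply is that little depends on these intervals. The section says: "The hypothesis testing of these additional secondary efficacy endpoints is considered exploratory". The study is described as a technical evaluation without power, neither percentage has a target, and the number of patients is plain to any reader. This stands and sets the weight of the point.

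The third is that the ICC is assumed, and that it may be low for spirometry quality. This also stands. The documents cannot show whether the shortfall is trivial or large, and peak flow is the better example.

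Finally, the interval proposed below is one adequate choice among several, and it too falls short near 0% or 100%. Both are conceded.

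**Conclusion.** The concern holds in its conditional form. No interval method is named for two percentages of repeated measurements from 12 patients, and a pooled binomial interval, exact or not, is too narrow under any positive within-patient correlation. With full completion and a rate of 80%, an ICC of only 0.05 brings coverage to about 81%, and an ICC of 0.3 to about 50%. With half the sessions done the figures are 89% and 66%. These sizes rest on assumed ICCs and rates and on a beta-binomial model. With no correlation there is no loss.

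The consequence is minor and the change is one to consider. The two point estimates, the primary endpoints and every endpoint that counts participants are unaffected.

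**What to change.** Add two or three sentences to Section 13:

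- Keep the pooled percentage p as the point estimate, so that neither endpoint changes. State whether a measurement is a session or a manoeuvre, and whether the training call counts.
- Base the 95% CI on the participant as the unit. One suitable form, with x_i of m_i measurements meeting the criterion in participant i and K contributing participants, is SE(p) = √[K/(K − 1) × Σ(x_i − m_i p)²] / Σm_i. The limits are logit(p) ± t(0.975, K − 1 df) × SE(p)/[p(1 − p)], transformed back so that they stay within 0 to 100%.
- Report the numbers of participants and of measurements, and list the per-participant percentages. If p is 0% or 100%, give the listing without this interval.
- Apply the same rule to any interval given for the alternative flow thresholds.

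The logit scale is preferable to a linear one. At a 90% rate and 24 sessions, the linear version covers 93 / 92 / 86 / 82% and has a limit above 100% in 55% / 85% of samples at ICC 0.3 / 0.5. A simple t interval on the 12 patient percentages is an acceptable alternative, though at an 80% rate its coverage falls to about 90% at ICC 0.5.

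No new data are needed. The cost is width: at an 80% rate and full completion the median total width is about 15 / 18 / 29 / 37 points at the four ICCs, against 9 for the pooled interval. With 12 participants coverage still drops when the rate is near 0% or 100% and correlation is high (92% / 88% at a 90% rate and 86% / 78% at a 95% rate, for ICC 0.3 / 0.5). This should be stated with the results.

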15.2. Patient Information and Informed Consent

Explanation of the study and informed consent will be obtained by a member of the study team. Patients shall be informed that participation is voluntary and that they may withdraw from the study at any time, without prejudice to their current or future care. Once all of their questions have been answered and they have voluntarily agreed to participate in the study, each patient will be asked to give verbal consent to participate following the UNC Guidelines for verbal consent. Informed consent must be obtained from each patient before the performance of any study-related activity.

15.3. Investigator Compliance

No modifications to the protocol shall be made without the approval of the IRB, except where the modification is necessary to eliminate an apparent immediate hazard to human subjects. Any departures from protocol must be fully documented in the source documentation and in a protocol deviation log.

15.4. ClinicalTrials.Gov Registration

As this study meets the FDAAA 801 definition of an “Applicable Clinical Trial”, it is required that the study be registered on ClinicalTrials.gov. The Principal Investigator will register and activate the study account prior to enrollment, and all results will be entered upon study completion, following statistical analysis, per the Results Database Guidelines.

16. References

1. US Government, Hospital Readmissions Reduction Program, Section 3025 Affordable Care Act. 2012.
2. Sheshadri A., et al. In submission. Personal communications. 2019
3. Stenzler A. Collecting Quality Spirometry at Home. *Respiratory Therapy* 2018; 13:48-54
4. Stenzler A. Improving home COPD monitoring through statistical process control (SPC). *Respiratory Therapy* 2019; 14:44-47.
5. Graham BL, et al. Standardization of Spirometry 2019 Update. An Official American Thoracic Society and European Respiratory Society Technical Statement ATS/ERS Guidance. *Am J Respir Crit Care Med.* 2019; 200 (8): e70-e88

17. Schedule of Assessments

Week	-1 to-2	1 ^a	2 ^a	3 ^a	4 ^a	5 ^a	6 ^a	7 ^a	8 ^a	9 ^a	10 ^a	11 ^a	12 ^a	13
Description	Screen	Enroll/ Training /Monitor	Monitor	Monitor	Monitor	Final Call								
Subject Consent	X													
Demographics	X													
Medical History	X													
Height and Weight	X													
Vital Signs	X	X ⁱ												X
Concomitant Medications ^e	X	X ⁱ				X				X				X
Forced Spirometry		X ^c	X ^c	X ^c	X ^c	X ^c	X ^c	X ^c	X ^c	X ^c	X ^c	X ^c	X ^c	
Slow Spirometry		X ^c	X ^c	X ^c	X ^c	X ^c	X ^c	X ^c	X ^c	X ^c	X ^c	X ^c	X ^c	
Oxygen Saturation		X ^h	X ^h	X ^h	X ^h	X ^h	X ^h	X ^h	X ^h	X ^h	X ^h	X ^h	X ^h	X
CAT Quality of Life Survey	X			X					X					X
COPD Action Plan ^f		X	X	X	X	X	X	X	X	X	X	X	X	X
Medication Adherence		X	X	X	X	X	X	X	X	X	X	X	X	X
Measurement Adherence	X	X	X	X	X	X	X	X	X	X	X	X	X	X
Nurse Call		X ^b				X ^b				X ^b				X
Adverse Events ^g		X				X				X				X
Usability Survey														X

Footnotes:

a Medication and measurement reminders issue 7 days a week, medication report cards on Fridays

b Nurse will call first week of monitored months. Will call second day after enrollment/training to assure patient understanding.

c Measured with GoSpiro. Collected post-bronchodilator. Slow spirometry Sunday, Monday, Wednesday, Friday and Saturday. Forced Spirometry Tuesday and Thursday. At home measurements occur in the morning at least 15 minutes following them taking their inhaled medications.

e Collected by Nurse on monthly call related to changes in inhaled medications, steroids or antibiotics.

f COPD Action Plan messages vary weekly according to the plan

g Adverse events confirmed on monthly nurse call plus any reported by patient or provider.

h Oxygen saturation measured 7 days a week, preceding spirometry measurements.

i Vital signs and concomitant medications from screening can be used for enrollment visit if conducted on same day.

18. Appendices

Appendix A: GoHome instructions

Appendix B: Measurement Instructions.

Appendix C: MTI CareBook – COPD Action Plan

Appendix D: Usability Questionnaire

Appendix E: CAT Questionnaire
